10.6.4. Marijuana Withdrawal Checklist

The MWC is a 22-item measure developed to assess the incidence and severity of marijuana withdrawal symptoms during the past 2 weeks. The MWC score is derived from the 22 items that are each rated on a 4-point scale from 0 (none) to 3 (severe). The MWC score ranges from 0 to 66 and is assessed at Baseline, end of Week 12, and safety follow-up visit.

Observed and change from baseline values for the MWC score will be summarized by treatment group and pooled JZP150 treatment groups by scheduled visit.

Jazz Pharmaceuticals
{Statistical Analysis Plan - Protocol #}JZP150-201-02

11. PHARMACOKINETIC ANALYSES

All study participants are required to provide blood samples for PK evaluation. The dosing regimen during the PK evaluation will be the participant's currently assigned treatment regimen. Blood samples for measurement of plasma concentration of JZP150 and its metabolites will be collected at the protocol-specified time points. Blood samples of 4 mL will be drawn at predose and 1 sample at 2 (\pm 15 minutes) hours post dose on Week 1 and Week 12, 5 (\pm 15 minutes) and 8 (\pm 15 minutes) hours post dose on Week 8.

11.1. Pharmacokinetic Concentrations

Descriptive statistics including number of participants, mean, SD, Min, median, Max, coefficient of variation (%CV), geometric mean, and geometric SD will be used to summarize the plasma concentration data of JZP150 and its metabolites including M21 and M22 by visit, time point and dose.

All statistical summaries and displays will be based on scheduled sampling times unless there are significant deviations of actual sampling times from scheduled sampling times. In calculation of the plasma concentration summaries, if concentration values are below the limit of quantitation, they will be set to zero.

Participants who are included in the PK summary but have missing data for a particular time point will not be included in the analysis for that time point. Unused data, measurements from excluded participants, unscheduled collections, or extra measurements will not be included in the summaries but will be presented in the participant data listings.

Plasma concentrations of JZP150 and its metabolites, if applicable, will be listed by participant, dose, visit, and scheduled sampling time. Actual sampling times will be included in the listing.

The exposure-response analysis may be conducted and reported separately.

Jazz Pharmaceuticals
{Statistical Analysis Plan - Protocol #}JZP150-201-02

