In single dose administration of 0.3 mg, JZP150 plasma levels were not above 1 ng/mL during most of the 24 hour period post dose; however, multiple dose administration of 0.5 mg QD resulted in mean plasma concentration levels in the 1 to 2 ng/mL range. Thus, based on these data and the observed between-subject variability, the 0.3 mg dose administered QD is not expected to maintain JZP150 plasma concentrations consistently above the threshold of 1 ng/mL to sustain the AEA levels at the target concentration above 2 to 2.5 ng/mL in most study participants. Therefore, the 0.3 mg dose should provide a means to identify a no-effect or minimally effective dose. Additionally, PTSD patients may have increased activity of FAAH and reduced levels of baseline AEA, and therefore may require higher AEA elevations compared with healthy volunteers. The 0.3 mg dose will also provide a low end of a broad range of concentrations to explore exposure-response.

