PK Analysis Set	The PK Analysis Set includes all participants who received at least 1 dose of study intervention and have at least 1 post-dose (post first dose) evaluable PK concentration. The PK set will be used to summarize the PK data, demographic and other baseline characteristics data, as well as exposure to study intervention.
PD Analysis Set	The PD Analysis Set includes all participants who received at least 1 dose of study intervention and have at least 1 pre-dose (prior to first dose) and 1 post-dose (post first dose) evaluable PD (AEA) level. The PD set will be used to summarize the PD data.

* Randomized participants from Site 1865 were excluded from this analysis set due to observed serious deviations and significant breaches to the principles of Good Clinical Practice during the study, particularly in the collection of efficacy data. These deviations and breaches are suspected to be gross misconduct and thus considered to have compromised the integrity of the efficacy data collected and reported by this site.

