10.3. Laboratory Assessments

The continuous clinical laboratory assessments (hematology, chemistry, urinalysis, [REDACTED]
 [REDACTED]) will be summarized in Safety Analysis Set using descriptive statistics by treatment group and pooled JZP150 treatment groups by scheduled visit.

Change from baseline to each post-baseline visit for clinical laboratory values is (value at the post-baseline visit) – (baseline value). If the laboratory value is missing at either baseline or a specific post-baseline assessment for a participant, change between baseline and that assessment is unknown.

Values for any of the clinical laboratory values parameters that are below or above the limit of quantification of the assay (BLQ or ALQ), will be summarized using the BLQ or ALQ threshold value; the actual reported value will be listed.

Shift tables will summarize changes in clinical laboratory results by scheduled visit with respect to the Baseline result. Laboratory values are categorized into L1, low, normal, high, or H1 based on the laboratory reference range. L1 and H1 values are predefined per the laboratory vendor alert ranges and correspond to the extreme abnormal lower and higher ranges, respectively.

Abnormal laboratory assessments deemed clinically significant by the investigator will be reported as an AE.

A listing of participants with abnormal value(s) according to the following criteria will be provided using the Safety Analysis Set:

- Any laboratory value that falls into the pre-defined low or high panic ranges (L1 or H1) per the ICON laboratory panic value chart.
- Alanine aminotransferase (ALT) or aspartate aminotransferase (AST) $\geq 3 \times$ Upper Limit of Normal (ULN) and total bilirubin $> 2 \times$ ULN
- AST or ALT $\geq 5 \times$ ULN,
- Creatinine $\geq 176 \text{ } \mu\text{mol/L}$
- Participants positive for alcohol, urine drug screen or pregnancy assessments

Jazz Pharmaceuticals
 {Statistical Analysis Plan - Protocol #}JZP150-201-02

All laboratory results, including pregnancy test, drug screen, and alcohol screen, will also be presented in participant data listings.

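### SAP 11.1 sets concentrations below quantitation to zero yet requires geometric mean and geometric SD, so one such value gives a geometric mean of 0 and no geometric SD

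*SAP*

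**What the plan says.** SAP 11.1 plans descriptive statistics for JZP150 and its metabolites, M21 and M22 among them, by visit, time point and dose. Besides n, mean, SD, minimum, median and maximum, the list includes "coefficient of variation (%CV), geometric mean, and geometric SD will be used to summarize the plasma concentration data". The next paragraph gives the only BLQ rule for these summaries: "if concentration values are below the limit of quantitation, they will be set to zero". It does not separate arithmetic from log-scale statistics and asks for no count of BLQ samples.

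Three neighbouring rules might be thought to settle the matter, but do not:

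- A participant with missing data at a time point "will not be included in the analysis for that time point" (SAP 11.1). A BLQ value that has been set to zero is not missing.
- Clinical laboratory values outside the assay range "will be summarized using the BLQ or ALQ threshold value" (SAP 10.3). That rule is confined to clinical laboratory parameters.
- The PK Analysis Set requires that participants "have at least 1 post-dose (post first dose) evaluable PK concentration" (SAP section 6). Whether a BLQ result counts as evaluable is not stated, and the rule selects participants, not samples.

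Protocol 8.5 and 9.4.7 give no BLQ rule, and SAP 7.7, which lists changes from the protocol, does not mention one.

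**The concern.** A geometric mean and a geometric SD are computed from logarithms, and zero has none. The stated rule therefore puts into the calculation the one value for which two of the listed statistics fail. The programmer must print a zero and a blank, drop the zeros, or choose a substitute value, and the SAP authorises none of the last two.

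BLQ values are plausible here. Troughs are sampled at Weeks 1 and 12, metabolites are summarised, some participants will miss doses, and the low dose was chosen to give low exposure: protocol 4.3 says that "the 0.3 mg dose administered QD is not expected to maintain JZP150 plasma concentrations consistently above the threshold of 1 ng/mL". In addition, "All study participants are required to provide blood samples for PK evaluation" (SAP section 11), so placebo samples are taken too, although SAP 11.1 does not say whether placebo forms a summary cell.

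At stake is the readability of the concentration tables that support a secondary PK objective, chiefly at the low end of exposure.

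**Working it through.** The plan states no figure for this point, so there is nothing to reproduce. The check has two branches.

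**Branch 1: the rule as written.** The geometric mean is (x1 × … × xn)^(1/n), or exp(mean of ln x). The geometric SD is exp(SD of ln x). Take one cell of 38 values, the number of 0.3 mg completers in protocol 9.2, with 37 positive values and one zero:

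- The product is 0, so the geometric mean is 0 whatever the other 37 values are.
- ln(0) is minus infinity, so the SD of the logs, and with it the geometric SD, is undefined. Direct computation returned 0 and not-a-number.

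This branch needs no assumption beyond one BLQ value in the cell.

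**Branch 2: zeros dropped when logs are taken.** The SAP does not state this; it is one thing that software may do. Assume lognormal concentrations with log-SD s = √ln(1 + CV²), and a share f below the limit. Let z be the standard normal quantile at f, φ the normal density, and λ = φ(z)/(1 − f). Then:

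- reported geometric mean / true geometric mean = exp(sλ)
- reported geometric SD = exp(s√(1 + zλ − λ²)), against a true value of exp(s)

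Assumed, not in the documents: CV of 40% (s = 0.385) to 100% (s = 0.833), and f from 1/38 to 40%.

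Worked case at f = 20%: z = −0.842, φ(z) = 0.280, λ = 0.280/0.80 = 0.350. The ratio is exp(0.385 × 0.350) = 1.14 at CV 40% and exp(0.833 × 0.350) = 1.34 at CV 100%.

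| BLQ share | λ | Geometric mean ratio, CV 40% | Ratio, CV 100% | Geometric SD, CV 40% (true 1.47) | Geometric SD, CV 100% (true 2.30) |
|---|---|---|---|---|---|
| 1 of 38 (2.6%) | 0.063 | 1.02 | 1.05 | 1.43 | 2.18 |
| 10% | 0.195 | 1.08 | 1.18 | 1.38 | 2.02 |
| 20% | 0.350 | 1.14 | 1.34 | 1.34 | 1.89 |
| 40% | 0.644 | 1.28 | 1.71 | 1.28 | 1.72 |

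**Check on a mixed rule.** Suppose zero is kept for the arithmetic mean while half the limit of quantitation (LLOQ/2) is used for the geometric mean. With a true geometric mean of 1, s = 0.5 and 45% BLQ, the arithmetic mean is 0.83 and the geometric mean 0.87. With s = 0.3 they are 0.70 and 0.81. A geometric mean cannot exceed the arithmetic mean of the same data, so such a table would contradict itself.

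**The case against.** The strongest reply is that little hangs on this. The PK objective is to be met by population PK modelling, exposure-response may be reported separately, and protocol 9.4.7 itself promises only listings of concentrations. Zeros would show as a minimum of 0, would enter the mean and median, and every concentration is listed by participant. That stands, and it is why the point is minor.

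Four stronger readings are tempting and are not supported:

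- A reader might infer that the trial's concentrations will be compared with 1 ng/mL, so that an error here would distort that comparison. Protocol 2.2 and 4.3 use 1 ng/mL only as background and dose rationale from earlier studies. Neither the protocol's PK sections nor SAP 11.1 plans such a comparison.
- A reader might infer that low exposure will be overstated. The SAP sets BLQ values to zero and does not say that they are dropped. Taken literally, the error goes the other way: the geometric mean collapses to 0.
- A reader might take the predose samples for pre-treatment samples that are BLQ by design. SAP Table 3, footnote f, shows that no PK sample is taken at baseline. All scheduled samples are at Weeks 1, 8 and 12, so predose means an on-treatment trough.
- A reader might take a BLQ share such as 20% as expected. The documents give no share and no assay limit. For parent drug they suggest that BLQ values may be few: protocol 2.2 reports steady state by Day 7 with 2- to 3-fold accumulation, and protocol 4.3 reports mean levels of 1 to 2 ng/mL on 0.5 mg daily.

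None of this removes the conflict inside SAP 11.1, which needs only one BLQ value in a cell.

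**Conclusion.** The point holds as a conflict within SAP 11.1. The zero rule and the two geometric statistics cannot both be applied in a cell that contains a BLQ value: the geometric mean is 0 and the geometric SD does not exist. That conclusion rests on the text alone.

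The percentages apply only if zeros are dropped, and they depend on the assumed lognormal shape, CV and BLQ share. They are illustrative: the bias is a few percent at one value in 38 and becomes material only when BLQ values are common. Cells without BLQ values are unaffected. No efficacy test is touched, and severity is low.

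**What to change.** In SAP 11.1:

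1. Limit the zero rule to the arithmetic statistics (mean, SD, %CV, minimum, median, maximum).
2. State one rule for the geometric statistics. For example, compute them on quantifiable values only, label them so, show their own n, and do not report them when more than a pre-stated share of the cell is BLQ. The label is essential, because the two kinds of mean then describe different sets of samples.
3. Print the number and percent BLQ for each visit, time point and dose.

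A stated positive substitute such as LLOQ/2 is an acceptable alternative, provided that the same value is used for the arithmetic statistics, so that the table stays coherent.

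SAP section 12 also asks for geometric mean and geometric SD for anandamide and gives no BLQ rule; the same wording could cover it.

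The cost is a sentence or two in the SAP and one row in the PK tables. No data collection or efficacy analysis changes.

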12. PHARMACODYNAMIC/BIOMARKER ANALYSES

Pharmacodynamic markers (e.g., AEA concentration) will be measured and descriptive statistics including the number of participants, mean, SD, Min, median, Max, %CV, geometric mean, and geometric SD will be used to summarize AEA levels by visit and treatment group. The Pharmacodynamic Analysis Plan may be provided in a separate document.

The pharmacodynamic-response analysis may be conducted and reported separately.

APPENDIX 1: PSQI (WITH PSQI-A) GLOBAL SCORE DERIVATION

The PSQI contains 19 self-rated questions and 5 questions rated by a bed partner or roommate (if one is available). Only self-rated questions are included in the scoring of the PSQI global score. The 19 self-rated items are combined to form seven component scores: duration of sleep, sleep disturbance, sleep latency, day dysfunction due to sleepiness, sleep efficiency, overall sleep quality, and need meds to sleep. Each of the component scores has a range of 0-3 points. In all cases, a score of “0” indicates no difficulty, while a score of “3” indicates severe difficulty. The seven component scores are then added to yield the PSQI global score, with a range of 0-21 (inclusive) points. A score of “0” indicates no difficulty and “21” indicates severe difficulties in all areas.

The component scores are calculated as follows:

Duration of Sleep:

Score is calculated based on number of minutes entered in Question 4: During the past month/week, how many hours of actual sleep did you get at night? as follows:

Value Provided	Score
≥ 7 hours of sleep (420 minutes)	0
≥ 6 hours of sleep (360 minutes) and < 7 hours of sleep (420 minutes)	1
≥ 5 hours of sleep (300 minutes) and < 6 hours of sleep (360 minutes)	2
< 5 hours of sleep (300 minutes)	3

This score will not be calculated if Question 4 is not answered.

Sleep Disturbance:

Score is calculated as a sum of the responses to Questions 5b) to 5j). Each question is rated on a 4-point scale from 0 (not during the past month/week) to 3 (three or more times a week/three or more days in the past week) and the responses are summed to derive the component score.

Sum of Scores	Score
0	0
1-9	1
10-18	2
19-27	3

This score will not be calculated if any of Questions 5b) to 5j) are not answered.

Jazz Pharmaceuticals
 {Statistical Analysis Plan - Protocol #}JZP150-201-02

Sleep Latency:

Score is calculated as a sum of the responses to Question 2 and Question 5a). Score for Question 2: During the past month/week, how long (in minutes) has it usually taken you to fall asleep each night? is calculated as follows:

Value Provided	Score
0-15 minutes	0
16-30 minutes	1
31-60 minutes	2
61-600 minutes	3

Question 5a) is rated on a 4-point scale from 0 (not during the past month/week) to 3 (three or more times a week/three or more days in the past week).

The responses to Question 2 and Question 5a) are summed to derive the component score.

Sum of Scores	Score
0	0
1-2	1
3-4	2
5-6	3

This score will not be calculated if any of Question 2 and Question 5a) are not answered.

Day Dysfunction due to Sleepiness:

Score is calculated as a sum of the responses to Question 8 and Question 9. Question 8 is rated on a 4-point scale from 0 (not during the past month/week) to 3 (three or more times a week/three or more days in the past week). Question 9 is rated on a 4-point scale from 0 (no problem at all) to 3 (a very big problem).

The responses to Question 8 and 9 are summed to derive the component score.

Sum of Scores	Score
0	0
1-2	1
3-4	2
5-6	3

This score will not be calculated if any of Questions 8 and 9 are not answered.

Jazz Pharmaceuticals
 {Statistical Analysis Plan - Protocol #}JZP150-201-02

Sleep Efficiency:

Score is calculated using the responses to the following questions:

- 1) Question 1: During the past month/week, what time have you usually gone to bed at night?
- 2) Question 3: During the past month/week, what time have you usually gotten up in the morning?
- 3) Question 4: During the past month/week, how many hours of actual sleep did you get at night?

A temporary value is calculated to assess sleep efficiency as follows:

- 1) If Question 3 > Question 1, $\text{Temp} = [\text{Question 4 (response in hours)} / (\text{Question 3 (time)} - \text{Question 1 (time)})] \times 100\%$
- 2) If Question 3 \leq Question 1, $\text{Temp} = [\text{Question 4 (response in hours)} / (24 + \text{Question 3 (time)} - \text{Question 1 (time)})] \times 100\%$

Depending on the Temp value, the component score is assigned as follows:

Temp Value (%)	Score
$\geq 85\%$	0
$\geq 75\% \text{ and } < 85\%$	1
$\geq 65\% \text{ and } < 75\%$	2
$\geq 0\% \text{ and } < 65\%$	3

This score will not be calculated if any of Questions 8 and 9 are not answered.

Overall Sleep Quality:

Score is calculated based on the response to Question 6: During the past month/week, how would you rate your sleep quality overall? The response is rated on a 4-point scale from 0 (very good) to 3 (very bad). This score will not be calculated if Question 6 is not answered.

Needs Meds to Sleep:

Score is calculated based on the response to Question 7: During the past month/week, how often have you taken medicine to help you sleep (prescribed “over the counter”)? The response is rated on a 4-point scale from 0 (not during the past month/week) to 3 (three or more times a week/three or more days in the past week). This score will not be calculated if Question 7 is not answered.

PSQI Global Score:

The PSQI global score (total sleep quality score) is the sum of the 7 component scores: duration of sleep, sleep disturbance, sleep latency, day dysfunction due to sleepiness, sleep efficiency,

Jazz Pharmaceuticals
{Statistical Analysis Plan - Protocol #}JZP150-201-02

overall sleep quality, and need meds to sleep. The range of the PSQI global score is from 0 to 21 (inclusive). The global score will not be calculated if at least one score involved into the calculation has no value.

PSQI Addendum Score:

The PSQI-A total score is derived from a sum of the 7 sleep disturbance items that are commonly reported by adults with PTSD (e.g., hot flashes, memories or nightmares of the traumatic experience, and episodes of terror during sleep) ([Germain et al 2004](#)). Items which are rated on a 4-point scale from 0 (not during the past month/week) to 3 (three or more times a week). A PSQI-A total score is obtained from the sum of the 7-items and has a range of 0-21, with higher scores indicating worse sleep disturbance.

Jazz Pharmaceuticals
{Statistical Analysis Plan - Protocol #}JZP150-201-02

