The change in participant-reported sleep problems as measured by the ISI, PSQI (with the PSQI-A) from Baseline to Week 12 will be analyzed using an MMRM model, separately for ISI, PSQI global score and PSQI-A total score. The model will include randomized treatment group, corresponding score at Baseline, week (as a discrete factor), treatment by week interaction, baseline by week interaction, and randomization stratum as fixed effects, and week as a repeated effect. An unstructured variance-covariance matrix will be used to model the correlation among repeated measurements. The modeling detail and SAS code are similar to [Section 9.1.2](#).

The ISI, PSQI (with PSQI-A) data will also be summarized by time point. For the PSQI (with PSQI-A) descriptive statistics for the 7 component scores will be provided time point.

Jazz Pharmaceuticals
 {Statistical Analysis Plan - Protocol #}JZP150-201-02

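### In SAP Appendix 1, the completeness rule for the PSQI sleep-efficiency component names Questions 8 and 9 instead of its own inputs, Questions 1, 3 and 4 (minor; component summary only)

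*SAP*

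**What the plan says.** SAP Appendix 1 builds the PSQI global score from seven components, each scored 0 to 3. For Sleep Efficiency it lists three inputs:

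- "Question 1: During the past month/week, what time have you usually gone to bed at night"
- "Question 3: During the past month/week, what time have you usually gotten up in the morning"
- "Question 4: During the past month/week, how many hours of actual sleep did you get at night"

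It continues: "A temporary value is calculated to assess sleep efficiency as follows". Hours slept are divided by time in bed, with 24 hours added when the rising time is not later than the bedtime. The resulting percentage (Temp) is placed in one of four bands. The completeness rule follows: "This score will not be calculated if any of Questions 8 and 9 are not answered".

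The same sentence stands under Day Dysfunction, where it fits: "Score is calculated as a sum of the responses to Question 8 and Question 9".

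For the global score, Appendix 1 says: "The global score will not be calculated if at least one score involved into the calculation has no value". SAP 9.2.6.6 analyses the global score by MMRM and says of the components that "descriptive statistics for the 7 component scores will be provided time point".

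**The concern.** A completeness rule should test the items that a score is built from. This one tests two items that play no part in sleep efficiency and omits the three that do. A programmer who follows the appendix literally will discard valid sleep-efficiency scores for participants who answered Questions 1, 3 and 4 but left Question 8 or 9 blank. The component's summary at that visit then rests on too few participants.

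There is also a gap. Questions 1 and 3 are used in no other component, so once this sentence points elsewhere, nothing in Appendix 1 says what happens when either is blank. Question 4 is covered, but only through the Duration of Sleep rule.

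**Working it through.** **Rules side by side (SAP Appendix 1)**

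| Component | Inputs | Questions named in the completeness rule |
|---|---|---|
| Duration of Sleep | 4 | 4 |
| Sleep Disturbance | 5b to 5j | 5b to 5j |
| Sleep Latency | 2, 5a | 2, 5a |
| Day Dysfunction | 8, 9 | 8, 9 |
| Sleep Efficiency | 1, 3, 4 | **8, 9** |
| Overall Sleep Quality | 6 | 6 |
| Needs Meds to Sleep | 7 | 7 |

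Six of the seven rules match their inputs; Sleep Efficiency does not.

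**The plan's own figure.** The global range is 7 × 0 = 0 to 7 × 3 = 21, as stated.

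**The formula uses only Questions 1, 3 and 4.** For bed 23:00, up 07:00 and 7 h slept, rising time is not later than bedtime on the clock. Temp = 7 / (24 + 7 − 23) = 7/8 = 87.5%, score 0. Questions 8 and 9 do not enter.

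**Enumeration.** Let each of Questions 1, 3, 4, 8 and 9 be answered or blank, with all other items answered. That gives 2^5 = 32 patterns.

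- *Component, rule as written:* Temp needs 1, 3 and 4, and the rule also needs 8 and 9. The component is available in 1 pattern.
- *Component, rule naming 1, 3 and 4:* Questions 8 and 9 may take any of 2 × 2 = 4 states. The component is available in 4 patterns.
- *Wrongly withheld:* 4 − 1 = 3 patterns (8 blank, 9 blank, or both blank, with 1, 3 and 4 answered).
- *Global score:* it needs Duration of Sleep (4), Day Dysfunction (8, 9) and Sleep Efficiency. Under either rule it is available only when all five are answered, which is 1 pattern. Difference: 0 of 32.

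These are counts of patterns, not probabilities.

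**Size at a visit.** If k participants answer Questions 1, 3 and 4 but leave 8 or 9 blank, the number behind the sleep-efficiency summary is short by k. The documents give no value for k. At k = 0 nothing changes. For any k, the component's count can never exceed the Day Dysfunction count, although the two draw on different items.

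**The case against.** The strongest reply is that this is a copying slip with almost no consequence. The components receive descriptive statistics only. SAP 7.2.5 says that, for multi-item questionnaires, the electronic platform blocks progress past a missing item, so blanks should be few. Most of this stands. The reservation is that the passage speaks of the rater and uses CAPS-5 as its example, whereas the PSQI is completed by the participant. Few blanks are likely but not assured.

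A reader might infer three stronger points, which the documents do not support.

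- *That the global score is corrupted.* When Question 8 or 9 is blank, Day Dysfunction is already missing, and the global score with it.
- *That a blank Question 1, 3 or 4 still yields a score.* Without all three there is no Temp. Every band has a lower limit, the lowest being 0%, so a value that does not exist falls in none. SAP 7.2.5 and 9.2.6 also rule out imputation for these endpoints.
- *That scoring efficiency above 100% as 0 is an error.* The top band has no ceiling: bed 01:00, up 06:00 and 6.5 h slept gives 6.5/5 = 130%, score 0. The band is nevertheless unambiguous, and the true band of an inconsistent answer is unknown, so 0 may be right. Setting only these cases to missing would be one-sided. If a 23:00 bedtime is entered as 11:00, with rising at 07:00 and 6 h slept, Temp is 6 / (24 + 7 − 11) = 30%, score 3, against 6/8 = 75%, score 1, when entered correctly. That error would stay in. Removing the high values would also cost the participant's global score, and so the other six components' contribution. Protocol 10.1.7 assigns quality checking to data management under separate guidelines, so the appendix's silence does not show that no check exists.

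**Conclusion.** The point holds as a minor scoring error. The Sleep Efficiency completeness rule is wrong as written, and no reading of the formula makes Questions 8 and 9 the relevant test. Its reach is one of seven component summaries, in 3 of 32 answered/blank patterns. The PSQI global score and its MMRM, and the primary and key secondary analyses, are unaffected.

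This conclusion assumes that the appendix is programmed literally and that no score is assigned where Temp cannot be computed. The number of participants affected is unknown and, given the platform described, probably small. The treatment of values above 100% is a matter of preference and forms no part of the finding.

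**What to change.** Under Sleep Efficiency in SAP Appendix 1, keep the sentence but replace Questions 8 and 9 with Questions 1, 3 and 4. This restores the pattern of the other six components and supplies the missing rule for Questions 1 and 3. Leave the Day Dysfunction sentence as it is. The cost is one line in an SAP amendment, the route that SAP section 3 already provides, and a check that the scoring program follows the corrected rule. No global score changes.

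Optionally, data management could query reported sleep longer than time in bed before database lock. Setting values above 100% to missing should not be required.
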